6.5.1 Acute (≤ 90 days from treatment start)

Expected adverse events include sore throat, hair loss, erythema of the scalp, headache, nausea and vomiting, lethargy, and transient worsening of neurological deficits. Reactions in the ear canals and on the ear should be observed and treated symptomatically.

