6.5.2 Late (> 90 days from treatment start)

Possible adverse events include radiation necrosis, cognitive dysfunction, visual difficulties, accelerated atherosclerosis, and radiation-induced neoplasms.

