11.1.5 Frequency of neurocognitive assessments

All tests will be given at baseline and at every follow-up for the first 6 months, then every 6 months thereafter (at 1, 3, 6, 12, 18, and 24 months). A window period of +/- 6 weeks will be allowed to correlate with each study time-point visit.

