11.2.2 Frequency of QOL assessment

The FACT-Br will be given at baseline and at every follow-up for the first 6 months, then every 6 months thereafter (at 1, 3, 6, 12, 18, and 24 months). A window period of +/- 6 weeks will be allowed to correlate with each study time-point visit.

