13.3 Statistical Analysis

Descriptive statistics will be performed on the clinical and treatment factors on subjects on this study. Categorical data will be presented on frequency tables while continuous data will be presented as mean, standard deviation, median and range. Local control, regional brain control, progression-free survival and overall survival will be assessed using the Kaplan-Meier method with censoring as appropriate. Univariate and multivariate analysis will be performed with these endpoints to determine patient factors that may influence outcome. These curves will also be compared to previously published results as historical controls. The results of the neurocognitive and quality of life surveys/tests will be plotted for each patient to assess for a general trend over time. The trend over time can also be analyzed by linear regression analysis. Each point in time can be compared with historical controls using a student's t-test to determine whether there is a significant difference in the survey/test scores in patients on our study versus historical results.

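### The only modelled summary of within-patient change in cognitive and QOL scores is a straight line, whose sign can depend on time on study if scores dip and then substantially recover

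*Combined protocol and SAP*

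**What the plan says.** Section 13.3 gives three analyses for the neurocognitive and QOL scores. Scores "will be plotted for each patient to assess for a general trend over time". Next, "The trend over time can also be analyzed by linear regression analysis". Finally, "Each point in time can be compared with historical controls using a student's t-test". The plots are a commitment; the regression and the t-tests are permitted but not required. No curved or categorical time term, no change-from-baseline summary and no handling of scores that stop early is named.

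Cognitive tests are at baseline and "at 1, 3, 6, 12, 18, and 24 months" (section 11.1.5). Section 11.2.2 gives the FACT-Br the same schedule. Each visit has a window of 6 weeks either side.

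Section 12.2 takes a patient off study at local CNS progression, death, hospice discharge or the patient's request.

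Among acute effects (up to 90 days) section 6.5.1 lists "transient worsening of neurological deficits". For the late period section 6.5.2 says "Possible adverse events include radiation necrosis, cognitive dysfunction".

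**The concern.** A straight line assumes one constant rate of change. A fall followed by recovery has no single rate, so the slope describes neither part. Patients will also leave at very different visits, and two patients on the same course can then have slopes of opposite sign only because one was followed longer.

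The plots carry no estimate, and the t-tests compare levels with an external group, not with the patient's own baseline. The slope is therefore the only planned modelled number for change within patients. Lower neurocognitive toxicity is part of the rationale in section 1.0, and objectives 2.2.3 and 2.2.4 rest on these scores. A positive slope could be cited in favour of the regimen when scores had fallen and only partly or just fully come back.

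**Working it through.** The plan states no effect size, SD or error rate for these endpoints and does not derive its 18 patients, so there is no planned figure to reproduce. The check applies the planned slope to the planned visits.

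**Inputs from the documents.** Visit times 0, 1, 3, 6, 12, 18, 24 months (11.1.5, 11.2.2); 18 patients (13.2); median survival of about 4 months for treated patients (1.0).

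**Assumptions.** The score profiles below. Median survivals of 8 and 12 months are also tried, because entry requires KPS of at least 70 and RPA class I or II.

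**Formula.** Slope b = Σ(t − t̄)y / Σ(t − t̄)², with y the change from baseline.

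**Profile A: 0, -3, -5, -3, 0, 0, 0.**

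- Followed to month 6: t̄ = 2.5; Σ(t − t̄)² = 6.25 + 2.25 + 0.25 + 12.25 = 21. Numerator = (-1.5)(-3) + (0.5)(-5) + (3.5)(-3) = 4.5 − 2.5 − 10.5 = -8.5. b = -8.5/21 = **-0.40** per month.
- Followed to month 12: t̄ = 4.4; Σ(t − t̄)² = 93.2. Numerator = (-3.4)(-3) + (-1.4)(-5) + (1.6)(-3) = 10.2 + 7.0 − 4.8 = 12.4. b = 12.4/93.2 = **+0.13**.
- Followed to month 24: t̄ = 64/7 = 9.14; Σ(t − t̄)² = 504.9. Numerator = 24.43 + 30.71 + 9.43 = 64.57. b = 64.57/504.9 = **+0.13**, or 0.128 × 24 = +3.1 points over 24 months.

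No score in profile A exceeds baseline. In the 24-month fit, months 1, 3 and 6 all lie before the mean time, so low scores there push the slope up. The sign depends on the shape and the visit times, not on the depth of the dip.

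**Other assumed profiles, slope per month by last visit**

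| Change from baseline at 0, 1, 3, 6, 12, 18, 24 | 6 | 12 | 18 | 24 |
|---|---|---|---|---|
| A. Full recovery by month 12 | -0.40 | +0.13 | +0.15 | +0.13 |
| B. 0, -5, -5, -3, -1, -1, -1 | -0.26 | +0.12 | +0.13 | +0.11 |
| C. 0, -3, -5, -4, -2, -2, -2 | -0.57 | -0.05 | +0.02 | +0.03 |
| D. Plateau: 0, -3, -5, -5, -5, -5, -5 | -0.74 | -0.31 | -0.18 | -0.12 |
| E. Dip, then late decline: 0, -3, -5, -3, -3, -5, -6 | -0.40 | -0.11 | -0.14 | -0.15 |

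A and B reverse sign clearly. C, with less recovery, ends close to zero. D and E stay negative, though D shrinks with longer follow-up. A steady decline has the same slope at every cut.

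**Pooled slope, profile A.** With 18 patients, exponential survival, and assumed SDs of 5 between and 3 within patients, the expected slope at median survival 4, 8 and 12 months is -0.04, +0.09 and +0.11. It was positive in 36%, 72% and 86% of 2,000 simulated trials each. Only death ended follow-up here.

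**Weight of each visit.** Leverage at 24 months = 1/7 + (24 − 9.14)²/504.9 = 0.58. In visit order the leverages are 0.31, 0.27, 0.22, 0.16, 0.16, 0.30, 0.58, which sum to 2. The last two hold 0.88/2 = 44%. The early visits are not negligible.

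**The case against.** Four points deserve weight.

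- **The early dip is assumed.** Section 6.5.1 speaks of neurological deficits, not of cognitive or QOL scores, and cognitive dysfunction is listed only as late. Objective 2.2.3 concerns long-term effects. A reader might infer that the protocol itself predicts an early cognitive dip; it does not. The listed acute effects, which include headache, nausea and lethargy, make a temporary fall plausible and no more. This stands.
- **The reversal needs substantial recovery.** A reader might infer that the slope has the wrong sign for late cognitive dysfunction. Profiles D and E do not support that. This stands.
- **The plan has other views of the data.** The plots would show a dip to a careful reader, and the t-tests keep visits apart. Misreporting requires someone to choose the optional slope and set the plots aside. This lowers the severity. It does not supply an estimate of change from the patient's own baseline.
- **A claim of improvement would be weak.** For profile A on its seven noiseless points, the 24-month slope has p = 0.18, and with a 4-month median survival the pooled slope is slightly negative. The risk is therefore mainly a misleading description, not a false significant finding.

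A further tempting argument, that the two last visits dominate the fit and the early ones hardly count, fails on the leverages above.

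**Conclusion.** The point holds in conditional form. If scores fall early and substantially recover, the slope in section 13.3 cannot show it, and its sign turns on time on study, which death, local progression or hospice can cut short. For profile A the change is from -0.40 per month at 6 months to +0.13 at 12 or 24 months, with every score at or below baseline. The conclusion rests on the assumed shape and on reading linear regression as a straight line in time, which is natural because no other term is named.

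It does not follow that the trial will report decline as improvement. The regression is optional, the plots are planned, and no decision rule uses the slope. This is a low-cost improvement to the analysis of secondary endpoints.

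**What to change.** In section 13.3, replace the linear trend by the mean change from each patient's own baseline at each visit, with a 95% CI and the number assessed. Give one early summary from months 1 and 3. Report month 6 onward visit by visit, labelled as results in patients still on study, and descriptively where few remain. Keep the individual plots.

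For profile A this returns -5 at month 3 whatever the later follow-up. Combining months 1 and 3 also avoids their overlapping windows: 6 weeks is about 1.4 months, so month 1 reaches to about 2.4 and month 3 starts at about 1.6. The early summary will not match the 90-day boundary exactly, since a month 3 score may fall at about 4.4 months.

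The cost is a sentence or two of text, with no new data, visits or patients. The downside is more estimates with wider intervals than a single slope. Under exponential survival with a 4-month median, 18 × 0.5^(3/4) = 10.7 patients would be alive at month 3, 6.4 at month 6 and 2.2 at month 12; with an assumed 8-month median, 13.9, 10.7 and 6.4. The late results still describe only those who remain, and this change does not cure that.

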1.0 INTRODUCTION/BACKGROUND

Brain metastases are the most common adult intracranial tumor, occurring in approximately 10% to 30% of adult cancer patients, and represent an important cause of morbidity and mortality in this population.¹ The risk of developing brain metastases differs with different primary tumor histologies, with lung cancer accounting for approximately one half of all brain metastases.² The prognosis of patients with brain metastases is poor. The median survival time of untreated patients is approximately 1 month.³ With treatment, the overall median survival time after diagnosis is approximately 4 months.⁴ The RTOG recursive partitioning analysis (RPA) describes three prognostic classes, defined by age, Karnofsky Performance Score (KPS), and disease status.⁵ The most widely used treatment for patients with multiple brain metastases is WBRT. The appropriate use of WBRT can provide rapid attenuation of many neurological symptoms, improve quality of life, extend median survival, and be especially beneficial in patients whose brain metastases are surgically inaccessible or when other medical considerations preclude surgery.^{6,7} The use of adjuvant WBRT after resection or stereotactic radiosurgery (SRS) has been proven to be effective in terms of improving local control of brain metastases, and thus, the likelihood of neurological death is decreased.⁸

The majority of patients who achieve local tumor control die from progression of extracranial disease, whereas the cause of death is most often due to CNS disease in patients with recurrent brain metastases.^{7,8} Currently, no consensus on the optimal radiation schedule for patients with brain metastases is established. Standard treatment regimens include dose fractionation schemes evaluated in the early RTOG studies and range from 20 Gy in 5 fractions to 40 Gy in 20 fractions. The exact regimen used is generally at the discretion of the treating physician and often depends upon issues such as the severity of CNS symptoms, the extent of systemic disease, and physician preference.

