3.0 PATIENT SELECTION

3.1 Inclusion Criteria

- 3.1.1 Pathologic proven diagnosis of solid tumor malignancy.
- 3.1.2 Age ≥ 18 .
- 3.1.3 KPS ≥ 70 .
- 3.1.4 Mini Mental Status Exam (MMSE) ≥ 18 prior to study entry.
- 3.1.5 RPA class I (KPS ≥ 70 , primary cancer controlled, age < 65 , metastases in brain only) or class II (lack of one or more of class I criteria) (see **Appendix A** for definitions).
- 3.1.6 One to ten brain metastatic lesions.

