12.2 Criteria for patient to be considered off study

- 12.1.1 Local CNS disease progression.
- 12.1.2 Patient death.
- 12.1.3 Patient request to come off study.
- 12.1.4 Patient is discharged to hospice

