13.2 Sample size

This will be a single cohort pilot study. Safety of the chosen dose level has been shown based on the previous phase I dose escalation iteration of this study.

18 patients will be enrolled consecutively into this single arm pilot study.

If a patient is not able to complete follow up to the toxicity assessment point of 4 months due to a toxicity judged not to be at least possibly related to therapy, then that patient will be replaced by the next patient enrolled.

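### The t-test against historical scores is not specified; if it pools variances and the two SDs differ, its error rate departs from nominal, and Welch's test avoids this at little cost

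*Combined protocol and SAP*

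**What the plan says.** Section 13.3 allows the neurocognitive and quality-of-life scores to be set against historical data visit by visit: "Each point in time can be compared with historical controls using a student's t-test". The stated purpose is "to determine whether there is a significant difference in the survey/test scores", and the comparison is of "patients on our study versus historical results". Section 13.1.2 lists both outcomes as secondary endpoints intended for comparison with historical controls.

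On size, Section 13.2 says "18 patients will be enrolled consecutively into this single arm pilot study". Scores are collected at baseline and "at 1, 3, 6, 12, 18, and 24 months" (Section 11.1.5, and the same times for FACT-Br in Section 11.2.2).

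Five things are not given: whether the test is one-sample, pooled two-sample or unequal-variance; its level and sidedness; which historical series supplies the scores; how many patients that series has; and the SD of any score in either group.

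**The concern.** A comparison of study patients with historical results reads most naturally as a two-sample test, and the two-sample Student's test assumes equal variances. With very unequal group sizes, the pooled SD is essentially that of the large group, while most of the uncertainty in the difference comes from the small one. If the small group's true SD is lower, the standard error is too large and real differences are missed. If it is higher, the standard error is too small and false differences appear.

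Nothing in the plan supports equal SDs. Entry limits such as "Mini Mental Status Exam (MMSE) ≥ 18 prior to study entry" and KPS of at least 70 could narrow the spread. Mixed histologies and one to ten lesions could widen it. The direction cannot be predicted.

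Reduced neurocognitive toxicity is part of the rationale in Section 1.0, and neurocognitive effects are an objective in Section 2.2.3. A significant or non-significant result against historical scores is therefore likely to be quoted.

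**Working it through.** The plan gives no figure to reproduce for this test, so the check is of its error rate when the true means are equal.

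**Inputs**
- Trial patients with a score, n₁: at most 18 (Section 13.2). The number at each visit is not given; 10 and 18 are used. For scale, Section 1.0 says that with treatment "the overall median survival time after diagnosis is approximately 4 months". If that applied with exponential survival, 18 × 0.5^(t/4) gives about 15, 11, 6 and 2 patients alive at 1, 3, 6 and 12 months. Patients with KPS of at least 70 may do better. Leaving the study for reasons such as "Local CNS disease progression" (Section 12.2) would remove more.
- Historical patients, n₂: not given; assumed 18, 50 and 200.
- r = trial SD divided by historical SD: not given; assumed 0.7, 1.0, 1.3 and 1.5.
- Level: not given; assumed two-sided 5%. Scores are taken as normal.

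**Pooled test, approximate formula** (historical SD = 1)
- True variance of the difference: V = r²/n₁ + 1/n₂.
- Variance the pooled test expects: P = [(n₁−1)r² + (n₂−1)]/(n₁+n₂−2) × (1/n₁ + 1/n₂).
- With k = √(V/P), error ≈ 2[1 − Φ(1.96/k)].

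For n₁ = 10 and n₂ = 200:
- r = 0.7: V = 0.049 + 0.005 = 0.054; P = (4.41 + 199)/208 × 0.105 = 0.1027; k = 0.725; error 0.7%.
- r = 1.3: V = 0.169 + 0.005 = 0.174; P = (15.21 + 199)/208 × 0.105 = 0.1081; k = 1.268; error 12%.
- r = 1.5: V = 0.225 + 0.005 = 0.230; P = (20.25 + 199)/208 × 0.105 = 0.1107; k = 1.442; error 17%.

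**Pooled test, simulation** (400,000 comparisons per cell)

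| Controls | Trial patients | r = 0.7 | r = 1.0 | r = 1.3 | r = 1.5 |
|---|---|---|---|---|---|
| 200 | 10 | 0.7% | 5% | 12% | 17% |
| 200 | 18 | 0.9% | 5% | 11% | 16% |
| 50 | 10 | 1.4% | 5% | 10% | 13% |
| 50 | 18 | 2.2% | 5% | 8% | 10% |
| 18 | 18 | 5% | 5% | 5% | 5% |

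Welch's test stays at 4.9–5.2% in all these cells. With only 5 trial patients it was 5.0–5.9%, over SD ratios from 0.5 to 2.

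**One-sample reading.** If the published mean is entered as a constant, nothing is pooled, but that mean's own sampling error is ignored. With equal SDs and 18 patients, the error is P(|T₁₇| > 2.110/√(1 + 18/n₂)):
- n₂ = 200: cut-off 2.110/1.044 = 2.02; error 5.9%.
- n₂ = 20: cut-off 2.110/1.378 = 1.53; error 14%.
- n₂ = 18: cut-off 2.110/1.414 = 1.49; error 15%.

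**The case against.** Four stronger conclusions are tempting, and the documents do not support them.

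- *The plan pools variances.* Section 13.3 names only a Student's t-test. Pooling is the usual two-sample reading, but a one-sample test also fits the words.
- *Few trial patients against many controls is enough to break the test.* It is not: with equal SDs the pooled error is 5% at every size, and with equal groups it stays close to 5% at every ratio. No historical series is named for these scores, so neither a large control group nor any particular SD ratio can be read from the plan. The MMSE limit bears on one of four instruments, and only at entry.
- *A stated 5% level is not delivered.* No level is stated; 5% is an assumption here.
- *This test is the only formal way to detect cognitive decline.* Section 13.3 also provides for linear regression of the trend over time. The t-test is only the named comparison of scores with historical controls.

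The two readings also fail in different settings. Pooling distorts most with a large historical group, where the one-sample test is nearly harmless (about 6% for 200 controls with equal SDs). The one-sample test is poor with a small group, where pooling does little damage.

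The wording is permissive, the endpoints are secondary, and no decision rule depends on the result. Larger problems with these comparisons lie elsewhere: unnamed and possibly non-comparable controls, selective survival to later visits, and multiplicity. Six visits by four instruments is 24 tests; 1 − 0.95²⁴ = 71% for at least one false positive if they were independent.

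All of this stands. It lowers the severity and makes the figures conditional. It does not supply a reason to prefer the named test, because either reading can miss its nominal level and the plan does not say which applies.

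**Conclusion.** The point holds conditionally and is minor. The distortion needs three things together: a pooled two-sample test, a historical group much larger than the trial group, and unequal SDs. Where they coincide, with 200 controls and a two-sided 5% level assumed, the error runs from about 1% (trial SD 0.7 times the historical) to 16–17% (1.5 times). With 50 controls the corresponding range is 1.4–2.2% to 10–13%. The documents cannot show whether these conditions will occur. They do show that the test is left unspecified where a safer standard alternative exists.

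**What to change.** In Section 13.3, replace Student's t-test by Welch's unequal-variance t-test, computed from the published mean, SD and n of a named historical source. Report each difference with its Welch 95% interval. Do not enter a published mean as a constant, and make no test where the source gives no SD or no n.

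The wording change is one line, but it obliges the sponsor to name a source with usable figures. The statistical cost is a small loss of power if the variances are in fact equal. For 10 against 200, the Welch degrees of freedom are about (0.1 + 0.005)²/(0.1²/9 + 0.005²/199) = 9.9, so the critical value is 2.23 instead of 1.97. For 18 against 200 it is 2.08 instead of 1.97.

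Welch's test corrects only the variance problem. It does nothing for non-comparable controls, selective survival to later visits or the number of tests.

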APPENDIX A

RTOG RPA Classification System

RPA Class I All of the following criteria:

KPS \geq 70%

Age $<$ 65 years

Absence of extracranial metastases

Controlled primary cancer

RPA Class II KPS \geq 70% **and**

One or more of the following criteria:

Age $>$ 65 years

Presence of extracranial metastases

Uncontrolled primary cancer

RPA Class III KPS $<$ 70%

APPENDIX B

CTCAE (Common Terminology Criteria for Adverse Events), version 4.02

The exact full criteria for toxicity assessment can be obtained at the NCI CTEP website at the following link:

http://evs.nci.nih.gov/ftp1/CTCAE/CTCAE_4.02_2009-09-15_QuickReference_8.5x11.pdf.

APPENDIX C – Evaluation Timeline

SEE BELOW

APPENDIX C - Timeline

Note:). A window period of +/- 6 weeks will be allowed to correlate with each study time-point and MRI visit.
